6 VARIABLES FOR ANALYSIS

6.1 Performance Variables

For the analysis of the performance variables the following analysis visits will be defined, since the primary evaluation of response shall be done 12 weeks after the last treatment or touch-up of the specific facial area. In Table 1 analysis visits for the responder analysis of Merz Nasolabial Folds Scale (MNLFS), Merz Marionette Lines Scale (MMLS) and Merz Upper Cheek Fullness Scale (MUCFS) are shown. All other performance variables will be analysed by the visits as specified in the case report form (CRF).

Table 1 Definition of the analysis visits for the response

Indication /Merz Aesthetic Scales	Analysis Visit	CRF Visit
All	Visit 2 (Week 4)	V2 (follow-up / optional touch-up)
Nasolabial folds / MNLFS	Week 12/16	
• V3 (week 12)/Primary endpoint visit if no touch-up at Visit 2 was done for neither left nor right nasolabial folds• V3a (week 16)/ Primary endpoint visit if touch-up at Visit 2 was done for left and/or right nasolabial folds but not for all other indications treated at V1• V3 (week 16)/ Primary endpoint visit if touch-up at Visit 2 was done for all indications treated at V1
Marionette lines/ MMLS	Week 12/16	
• V3 (week 12)/Primary endpoint visit if no touch-up at Visit 2 was done for neither left nor right marionette lines• V3a (week 16)/ Primary endpoint visit if touch-up at Visit 2 was done for left and/or right marionette lines but not for all other indications treated at V1• V3 (week 16)/ Primary endpoint visit if touch-up at Visit 2 was done for all indications treated at V1
Cheek fullness / MUCFS	Week 12/16	
• V3 (week 12)/ Primary endpoint visit if no touch-up at Visit 2 was done for neither left nor right cheek fullness• V3a (week 16)/ Primary endpoint visit if touch-up at Visit 2 was done for left and/or right cheek fullness but not for all other indications treated at V1• V3 (week 16)/ Primary endpoint visit if touch-up at Visit 2 was done for all indications treated at V1
All	Visit 4 (Week 24/28)	V4/Follow-up (12 weeks after previous visit)
All	Visit 5 (Week 48/52)	V5/Follow-up (24 weeks after previous visit)
All	Visit 6 (Week 72/76)	V6/Final study visit (24 weeks after previous visit)

6.1.1 Primary Performance Variable(s)

The primary performance variables of this study are:

- Responder rate for **nasolabial folds** after treatment with RADIÉSSE® (+) Lidocaine based on the blinded rater's evaluation on the MNLFS. Response defined as improvement of ≥ 1 point in both folds (left and right) from Day 1 pre-injection to Week 12/16 (depending on touch-up).
- Responder rate for **marionette lines** after treatment with RADIÉSSE® (+) Lidocaine based on the blinded rater's evaluation on the MMLS. Response defined as improvement of ≥ 1 point in both marionette lines (left and right) from Day 1 pre-injection to Week 12/16 (depending on touch-up).
- Responder rate for **cheek fullness** after treatment with RADIÉSSE® (+) Lidocaine based on the blinded rater's evaluation on the MUCFS. Response defined as improvement of ≥ 1 point in both cheeks (left and right) from Day 1 pre-injection to Week 12/16 (depending on touch-up).

6.1.2 Secondary Performance Variables

[figure not shown]
The secondary performance variables are defined as follows:

[figure not shown]
- Responder rate for nasolabial folds after treatment with RADIÉSSE® (+) Lidocaine based on the blinded rater's evaluation on the MNLFS prior to optional touch-up at V2 (Week 4), at Week 24/28, at Week 48/52, and at Week 72/76 (depending on touch-up performed). Response for nasolabial folds defined as improvement of ≥ 1 point in both folds (left and right) compared to Day 1 pre-injection.
- Responder rate for marionette lines after treatment with RADIÉSSE® (+) Lidocaine based on the blinded rater's evaluation on the MMLS prior to optional touch-up at V2 (Week 4), at Week 24/28, at Week 48/52, and at Week 72/76 (depending on touch-up performed). Response for marionette lines defined as improvement of ≥ 1 point in both marionette lines (left and right) compared to Day 1 pre-injection.
- Responder rate for cheek fullness after treatment with RADIÉSSE® (+) Lidocaine based on the blinded rater's evaluation on the MUCFS prior to optional touch-up at V2 (Week 4), at Week 24/28, at Week 48/52, and at Week 72/76 (depending on touch-up performed). Response for cheek fullness defined as improvement of ≥ 1 point in both cheeks (left and right) compared to Day 1 pre-injection.
- Treating investigator's evaluation of the global aesthetic improvement on the Investigator Global Aesthetic Improvement Scale (iGAIS) from Day 1 pre-injection photos to V2 (Week 4) prior to optional touch-up, to Week 12/16, to Week 24/28, to Week 48/52, and to Week 72/76 (depending on touch-up performed).
- Subject's evaluation of the global aesthetic improvement on the Subject Global Aesthetic Improvement Scale (sGAIS) from Day 1 pre-injection photos to V2 (Week 4)

prior to optional touch-up, to Week 12/16, to Week 24/28, to Week 48/52, and to Week 72/76 (depending on touch-up performed).

6.2 Safety Variables

6.2.1 Primary Safety Variable(s)

The primary safety variable is:

- Occurrence of treatment emergent adverse events (TEAEs).

6.2.2 Secondary Safety Variables

Not applicable.

CONFIDENTIAL
Template: tem-sap-v5-20170522
File name: M900391005-sap-v1.0 Final-2019-07-30.docx

[REDACTED]

[REDACTED]

[REDACTED]

[REDACTED]

[REDACTED]

[REDACTED]

7 STATISTICAL ANALYSIS METHODS

7.1 Performance Variables

All performance analyses will be based primarily on the FAS and additionally for primary performance analyses on the PPS. Where applicable, subgroup analyses will be performed on the following subpopulations “nasolabial folds”, “marionette lines” and “cheek volume loss”. Statistical tests will be one-sided hypothesis tests for responder rates. The Bonferroni Holm alpha correction will be used for three statistical testes to adhere to the global significance level of 0.025.

Continuous variables (values and changes from baseline) will be summarized by number of non-missing values (n), mean, standard deviation (SD), median, quartiles, minimum, and maximum. For qualitative variables, absolute and percent frequencies (n, %) will be displayed. The responder analyses the percentage will be based on the number of subjects in respective indication group. The percentage of all other analyses will be based on the number of observed values. Confidence limits and descriptive p-values will be given, where appropriate.

For performance variables the measurement at V1 (Day 1) is defined as baseline value.

P-values will be reported to four decimal places (e.g., p=0.0375). P-values below 0.0001 will be presented as ‘<0.0001’.

Mean, first quartile (Q1), median, and third quartile (Q3) will be reported to one decimal place more than the data were collected, for the standard deviation two decimal places more will be displayed; for derived data, an adequate number of decimal places will be chosen. Percentages will be calculated using the denominator of all subjects in a specified population and treatment group. The denominator will be specified in a footnote to the tables for clarification if necessary. Percentages will be reported to one decimal place.

7.1.1 Primary Performance Variable(s)

For the primary performance analyses, responder rates for nasolabial folds, for cheek volume loss, and for marionette lines will be summarized as absolute and percent frequencies (n, %). The denominator for each response will be the number of subjects in the analysis set treated in the indication. Only the subjects of the FAS treated for the corresponding indication will be included into the analyses of responder rates. Any subject with missing assessment will be evaluated as non-responder in the FAS. Subjects with missing assessments with respect to the primary performance variables will be excluded from the PPS.

The aim of primary performance analyses is to show that there are:

- significantly more than 60% of responders in treatment of nasolabial folds

- significantly more than 60% of responders in treatment of marionette lines
- significantly more than 60% of responders in treatment of cheek volume loss

A confirmatory exact one-sample binomial test will be used to test probability of being a responder (p) is above 60% separately for each indication:

- $H_0 \text{ nasolabial folds: } p \leq 0.6$ vs. $H_1 \text{ nasolabial folds: } p > 0.6$
- $H_0 \text{ marionette lines: } p \leq 0.6$ vs. $H_1 \text{ marionette lines: } p > 0.6$
- $H_0 \text{ cheek volume loss: } p \leq 0.6$ vs. $H_1 \text{ cheek volume loss: } p > 0.6$

Using the Bonferroni Holm alpha correction with global significance level of 0.025 for the test with lowest p-value the local significance level α_1 is 0.0083. For the test with the second lowest p-value α_2 is 0.0125. For the test with the highest p-value α_3 is 0.025. If the lowest p-value of a single (one-sided) hypothesis is below 0.0083 it is shown that the responder rate lies significantly above 60% for this indication. In this case performance is shown for this indication. If additionally the second p-value of a single (one-sided) hypothesis is below 0.0125 it is shown that the responder rate lies significantly above 60% also for this indication. If additionally the highest p-values of the single sub-hypothesis are below 0.025, the primary objective regarding performance (i.e., performance shown for all three indications) can be concluded. The procedure is stopped if a p-value is higher than the corresponding local significance level. In this case no subsequent null hypothesis will be rejected.

Point estimates of the rates will be provided with exact one-sided 97.5% Clopper-Pearson confidence intervals. The following SAS code will be used:

```
proc freq data = dataset order = freq;
  tables response / binomial (p=.6) exact cl alpha=.05;
  exact binomial;
run;
```

Confirmatory testing will be performed on the FAS with missing response imputed as non-responder. Furthermore, sensitivity analysis on PPS (observed case) will be performed.

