- An important untoward occurrence for any implant material is the introduction of the product into the blood vessels, which may lead to embolization, occlusion of the vessels (vascular compromise), ischemia, or infarction which can lead to necrosis, cerebral ischemia or cerebral hemorrhage, leading to stroke, and damage to underlying facial structures. In rare cases, such embolization can lead to blindness, especially when the dorsum of the nose is treated [Rayess 2017]. In this study, nose correction is not allowed and only well trained and experienced physicians with a deep knowledge of the facial anatomy will be included in this study. The investigator is advised to take extra care during the procedure. He/she needs to inject the SMD slowly and apply the least amount of pressure necessary. If some subject exhibits symptoms of blanching of the skin or unusual pain during or shortly after the procedure, subjects should receive prompt medical attention and evaluation by an appropriate health care practitioner specialist.

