## 6.2 Discussion of study design, including choice of control groups

The prospective, open label multicenter PMCF study design was chosen to adequately investigate the performance and safety of the SMD as per the current practice.

In general, prospective designs can achieve a higher data quality as compared to retrospective designs.

In order to collect “real-life” data, it has been decided not to interfere with investigators’ usual practice and therefore employ a PMCF design. This design will allow evaluation of performance and safety of the SMD while used as per its current approved IFU.

Using several study sites increases the representativeness of the study results and decreases study site-related biases.

The observational period of approximately 18 to 19 months (if touch-up has been performed) was chosen to allow assessment of late-onset reactions.

The volume of the SMD to be injected as well as the choice of the injection technique are at the discretion of the investigator. This reflects the common use of fillers among physicians because the volume is adapted to the depths and the size of the areas to be treated as well as to the quality/thickness of the skin in these areas. Moreover, it depends on the desired cosmetic outcome which is usually a collective decision of both the treating physician and the subject.

Investigators should use only the needles provided in the SMD packaging, however, investigators are allowed to use cannulas at their own choice instead of the supplied needles, if cannulas instead of needles are usually being used in their daily practice. As this is a PMCF study with the main focus on performance and safety under real life conditions in daily practice, a control group that will be left untreated is not foreseen.

A blinded rater at each study site not otherwise involved in study procedures was chosen to assess the primary endpoint. The blinded rater does not know which indications were treated, which helps minimize the possible effects of evaluator bias.

 - confidential -	Merz Pharmaceuticals GmbH	M900391005/RaLido
	Clinical Protocol for post market clinical follow-up studies (PMCF)	

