3 CLINICAL STUDY DESIGN AND OBJECTIVES

3.1 Clinical Study Design

This study is an open-label, multicenter, uncontrolled, post-market clinical follow-up (PMCF) study with a rater-blinded live evaluation. There will be no control group as the objective is to confirm safety and performance in “real-life”. Approximately 175 subjects per indication seeking for dermal filler/volumising treatment in the face, who agree to participate by signing the written informed consent form and who are fulfilling inclusion/exclusion criteria will be enrolled at approximately 15-20 sites.

Since subjects must be treated for at least two and up to three indications, selected out of nasolabial folds, marionette lines and cheek volume loss, and since it is planned to collect and analyze data from about 175 subjects per separate indication, about 210 subjects in total are planned to be enrolled.

Assuming that 50% of subjects will be treated for two and 50% for three indications respectively, at least 105 subjects will be treated in all of the three indications (i.e. nasolabial folds, marionette lines, and cheek volume) and 35 subjects will be treated in one of the possible treatment combinations:

- Nasolabial folds + marionette line;
- Nasolabial folds + cheek volume;
- Marionette lines + cheek volume.

If the number of subjects treated in all of the three indications is higher than 105, the number of subjects treated for only two indications may be reduced so that the total number of all treated subjects will be 210 but the aim to treat 175 subjects for each of the indications will be reached.

The duration of the study per subject is approximately 18 months (in case of no touch-up performed at Visit (V) 2) and 19 months (in case of touch-up performed at V2).

The study medical device (SMD) is CE-marked in Europe since 02-JUN-2016 and will be injected as per its current approved labelling and investigator's usual practice at Day 1 with an optional touch-up treatment after 4 weeks.

The subject will be injected at Day 1 with volume for each area to be treated, using injection techniques based on investigator's judgement, skin condition, safety and subject's expectations. A minimum of two and a maximum of three indications (nasolabial folds, marionette lines, cheeks) per subject can be treated. An optional touch-up can be performed after four weeks at V2 in the indications that were treated at Day 1, to obtain an optimal aesthetic outcome, as appropriate.

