7.4.5 Examination of Subgroups

The subpopulation “nasolabial folds” will contain all subjects treated for nasolabial folds, regardless if they have been treated for one or both other indications as well. The subpopulation “marionette lines” will contain all subjects treated for marionette lines, regardless if they have been treated for only one or for two other indications as well. The subpopulation “cheek volume loss” will contain all subjects treated for cheek volume loss, regardless if they have been treated for one or both other indications as well. Each of these three subpopulations will contain approximately 175 subjects. Each subject will belong to at least two of these subpopulations. At least 50% of the subjects will be treated in all of the three indications and as consequence these subjects will belong to all of these three subpopulations (i.e. nasolabial folds, marionette lines, and cheek volume loss).

For the performance variables iGAIS, sGAIS, [REDACTED] [REDACTED] for subject dispositions, [REDACTED] [REDACTED], and for all safety analyses (analysis of TEAEs), subgroup analyses will be performed for each indication (subjects treated for nasolabial folds, for marionette lines and/or for cheek volume loss) in addition to the total population.

Responder analysis of MNLFS, MUCFS, and MMLS will only be performed for the subpopulations and not for the total population. [REDACTED] [REDACTED]

[REDACTED]™ – Satisfaction with Cheeks will only be analysed for the subpopulation “cheek volume loss”.

[REDACTED]

7.4.6 *Pooling of sites*

Not applicable.

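### Do the exact binomial tests need an adjustment, or an added limit, for clustering of responders within sites?

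*SAP*

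**What the plan says.** SAP 7.1.1 sets one test per primary variable: "A confirmatory exact one-sample binomial test will be used to test probability of being a responder (p) is above 60% separately for each indication". For estimation, "Point estimates of the rates will be provided with exact one-sided 97.5% Clopper-Pearson confidence intervals". The PROC FREQ code shown there uses a single response variable and no site variable. The only other readable analysis of the primary variables is on the per protocol set: "Furthermore, sensitivity analysis on PPS (observed case) will be performed".

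SAP 3.1 states that subjects "will be enrolled at approximately 15-20 sites". SAP 7.4.6, headed "Pooling of sites", is marked not applicable, and the readable subgroups in SAP 7.4.5 are by indication only.

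Protocol 6.2 explains the multicentre design: "Using several study sites increases the representativeness of the study results and decreases study site-related biases". On assessment it adds: "A blinded rater at each study site not otherwise involved in study procedures was chosen to assess the primary endpoint". Injection volume and technique are left to the treating investigator (Protocol 6.2 and 8.1.1.2). Protocol 4.3 describes who takes part: "only well trained and experienced physicians with a deep knowledge of the facial anatomy will be included in this study".

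**The concern.** The exact binomial distribution holds only if subjects respond independently with a common probability. Here, subjects at one site are likely to share an injector, a technique and a rater, so their outcomes may be correlated. Positive correlation makes the variance of the overall rate larger than binomial. The nominal levels of 0.0083, 0.0125 and 0.025 would then not hold, and the lower limits would sit too high.

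The study is uncontrolled, so the whole performance claim is a rate and its lower limit against a fixed 60%. No comparator within the site cancels a site effect. If an observed rate fell only a little above the pass mark, a reader could not tell from the readable outputs whether a few sites carried it. SAP Section 4 does mention independence in its power statement, but that concerns the three tests, not subjects within sites.

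**Working it through.** **Inputs from the documents (SAP Sections 3.1 and 4).** Null rate 0.60; expected rate 0.75; one-sided local levels 0.025/3, 0.025/2 and 0.025; 140 subjects required and 175 planned per indication; 15-20 sites. Equal enrolment would give 175/20 = 8.75 to 175/15 = 11.7 subjects per site.

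**Assumed, not in the documents.** ICC 0.01 to 0.10. With site rates varying about 0.60, the SD of true site rates is √(ICC × 0.6 × 0.4): 0.049 at ICC 0.01 and 0.155 at ICC 0.10.

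**1. The plan's own power.** At n = 140 the smallest counts with P(X ≥ r | 0.6) at or below the local levels are 99, 98 and 96. P(X ≥ r | 0.75) is 0.896, 0.926 and 0.966, and the product is 0.801. These match the SAP. At n = 175 the counts are 121, 120 and 119, with power 0.967, 0.978 and 0.985.

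**2. Sites random, true rate 60%.** Responders at each site follow a beta-binomial distribution; the total is the exact convolution over sites. Each cell gives 20 sites / 15 sites.

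| ICC | P(121 or more), level 0.0083 | P(120 or more), level 0.0125 | P(119 or more), level 0.025 |
|---|---|---|---|
| 0 | 0.0077 | 0.0118 | 0.0177 |
| 0.01 | 0.0098 / 0.0106 | 0.0146 / 0.0157 | 0.0213 / 0.0227 |
| 0.05 | 0.0198 / 0.0251 | 0.0273 / 0.0338 | 0.0370 / 0.0447 |
| 0.10 | 0.0346 / 0.0462 | 0.0449 / 0.0581 | 0.0574 / 0.0722 |

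At ICC 0.01 the last step stays below its nominal level, and the first two exceed theirs by about 0.002 to 0.003.

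**3. Sites fixed.** Take the same spread of site rates, held fixed with a size-weighted mean of 60%. Simulation (300,000 runs per setting) gives 0.005-0.007 for 121 or more and 0.013-0.017 for 119 or more. There is no inflation, because a sum of independent binomials with unequal rates varies no more than one binomial at their mean.

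**4. At the planned rate.** The design effect is 1 + (m − 1) × ICC, where m is subjects per site. For 15 sites and ICC 0.05 it is 1 + 10.67 × 0.05 = 1.53, so the effective n is 175/1.53 = 114. A Clopper-Pearson limit at effective n, for 131/175 (74.9%), is 0.678 with no clustering, 0.659-0.664 at ICC 0.05 and 0.643-0.651 at ICC 0.10. All exceed 0.60. Using the random-site model of step 2 with a true rate of 75%, power at ICC 0.10 is still at least 0.90 at every local level.

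**5. Where the reading could change.** On the same effective-n basis, the smallest count whose 97.5% limit exceeds 0.60 is 119 (68.0%) with no clustering, 121-122 at ICC 0.05 and 123-125 (70.3-71.4%) at ICC 0.10. The sensitive band at this level is therefore about 68% to 71%.

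**6. What a clustered limit would bring.** The version examined works on the logit scale, with cluster-robust variance, factor k/(k−1), and t on k−1 degrees of freedom for k sites. With no clustering at all, 119 or more respond but this limit fails to exceed 60% in 4.9-6.9% of trials at a true 70%, and in 0.9-1.4% at 75%. The reverse disagreement occurs in 3.6-3.7% and about 0.4%. Its simulated level is about 0.023 with equal sites and 0.026-0.029 when half the sites are about three times larger. With a more skewed assumed pattern of 15 sites (40 subjects at the largest, 2 at the smallest) it is about 0.03 at ICC 0 and 0.038-0.041 at ICC 0.05-0.10, against 0.025.

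**The case for a change.** The best case for acting is that the additions cost almost nothing. Site is already recorded, the test, Holm procedure and sample size would stay, and the output would be labelled descriptive. Protocol 6.2 appeals to representativeness, which invites reading the sites as a sample of wider practice. On that reading the inflation at ICC 0.05 or more is real: about 2.4 to 3 times the first Holm level and 1.5 to 1.8 times the last. With skewed site sizes and ICC 0.05-0.10, the exact test reaches 0.068-0.114 at the last step. The clustered limit, imperfect as it is, does better there.

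The arithmetic stands, and so does the observation that no readable text reports results by site. The step from there to a fault in the plan does not stand. The upper ICC values are the less plausible ones, given the documents' own features:

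- all sites treat towards at least a 1-point improvement (Protocol 8.1.1.2 and 9.5), and a touch-up is allowed (8.2.4);
- raters and investigators are trained (9.2.2), and standardization among sites is planned (11.1);
- the same rater should score a subject throughout (9.2), so constant leniency largely cancels in a change from baseline.

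The representativeness sentence is a design rationale, not a statement that sites are random draws, and Protocol 4.3 restricts participation to experienced physicians.

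**Conclusion.** No change to the plan is needed. Treating subjects as independent is a conventional choice for an exact single-arm test, and nothing in the confirmatory analysis is shown to be wrong as written. Any inflation needs two things the documents do not supply: an appreciable ICC, and inference to a population of sites. If either is absent the problem disappears or is very small. If both hold, with ICC up to 0.10 and equal sites, the conclusion at the planned 75% still stands on average, and the effect is mainly confined to observed rates of about 68% to 71%.

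The clustered limit offers no clear gain. Statisticians would disagree on fixed or random sites and on the method for 15-20 clusters. It can contradict a passing exact result by noise alone. A duty to report when it does not exceed 60% would make it a second pass mark, matched only to the last Holm level.

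A descriptive table of responders by site is a reasonable reporting choice under either reading, and an analyst can produce it without amending the SAP. It may already be planned: SAP 7.4.2 refers to tables and listings in an appendix, SAP Section 2 to the sponsor's standard output set, and parts of SAP 6, 7.1.2 and 7.4.5 and both appendices are redacted. These cannot be checked, so the absence of site reporting is established for the readable text only.

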4 DETERMINATION OF SAMPLE SIZE

The sample size estimation is based on the primary performance analyses, i.e., on three one-sided exact one-sample binomial tests (one test for each indication). Under the following assumptions 140 subjects are required per indication to reach a global power of 80%:

- Global significance level: 0.025 (one-sided)
- Local significance levels for tests per indication: $\alpha_1 = 0.0083$, $\alpha_2 = 0.0125$, $\alpha_3 = 0.025$ (Bonferroni Holm adjusted alpha)
- Proportion of responders under the null hypothesis 0.6
- Expected responder rate under test treatment: 0.75
- Power for each single test: 89.6% (for α_1), 92.6% (for α_2), 96.6% (for α_3)
- Global power for all tests under independence 80.1%

In order to have sufficient subjects for safety analysis the sample size is increased to 175 subjects per indication so that a minimum of 161 subjects per indication will complete the study. In 161 subjects per indication an adverse event (AE) with a true incidence of 1% will be observed at least once per indication with a probability of 80%. The total number of 210 subjects to be treated was chosen to have approximately 175 subjects treated per indication.

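### The SAS code prescribed for the confirmatory test fixes neither the responder category nor the upper tail, so it does not guarantee the stated test of a responder rate above 60%

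*SAP*

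**What the plan says.** SAP 7.1 states that "Statistical tests will be one-sided hypothesis tests for responder rates". SAP 7.1.1 gives the direction: the exact binomial test is to "test probability of being a responder (p) is above 60% separately for each indication", with H0: p ≤ 0.6 against H1: p > 0.6 for nasolabial folds, marionette lines and cheek volume loss. Holm's procedure then compares the ordered one-sided p-values with 0.0083, 0.0125 and 0.025.

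The same section promises point estimates of the rates with exact one-sided 97.5% Clopper-Pearson limits, and says "The following SAS code will be used". The two lines that matter are "proc freq data = dataset order = freq" and "tables response / binomial (p=.6) exact cl alpha=.05". The first orders the response levels by observed frequency. The second gives the null value 0.6 and an alpha for the interval. Neither names the responder level or a tail. The visible text does not say how the response variable is coded or which printed p-value enters Holm's procedure.

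**The concern.** The hypothesis fixes the category (responders) and the direction (above 60%). The code fixes neither. With frequency ordering and no named level, the data decide which category comes first. With no tail specified, the code does not ensure that the one-sided p-value is the upper-tail one.

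This matters when an indication performs poorly. Holm's procedure ranks and rejects on the size of the p-value. If the printed value were carried into it unchecked, an indication that clearly fails could be declared successful, and its misdirected p-value could rank first among the three. Missing assessments count as non-response in the FAS, which moves observed rates down towards the affected range. Apart from the p-value, the estimate and limits printed below 50% response would belong to non-responders, although the SAP promises them for the responder rates.

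**Working it through.** **Inputs.** SAP 4 and Protocol 12.1: null rate 0.6, expected rate 0.75, 140 subjects per indication for power, 175 planned, 161 expected to complete. SAP 7.1.1 and 7.4.4: local levels 0.025/3 = 0.0083, 0.025/2 = 0.0125, and 0.025.

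**Step 1: reproduce the plan's power.** Take the smallest r with P(X ≥ r | 140, 0.6) at or below the level, then compute P(X ≥ r | 140, 0.75).

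| Level | r | Type I error at 0.6 | Power at 0.75 |
|---|---|---|---|
| 0.0083 | 99 | 0.0055 | 89.6% |
| 0.0125 | 98 | 0.0091 | 92.6% |
| 0.025 | 96 | 0.0225 | 96.6% |

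The product is 80.1%. All four stated power figures reproduce, so the planning assumes an upper-tail test on responders. At n = 175 the same test needs 121, 120 and 119 responders.

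**Step 2: model the code.** Two assumptions about PROC FREQ are needed. They are not in the documents, and SAS was not run.

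- (A) The binomial option tests the first listed level. Under frequency ordering, x responders out of n give a tested count y = max(x, n − x).
- (B) The one-sided exact p-value follows the data: P(Y ≥ y | n, 0.6) if y/n > 0.6, otherwise P(Y ≤ y | n, 0.6).

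A wrong pass is a count x for which the printed p-value is below the level while the correct P(X ≥ x | n, 0.6) is not.

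**Step 3: examples at n = 175.**

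| Responders | Tested count | Tail | Printed p | Correct p |
|---|---|---|---|---|
| 122 (69.7%) | 122 responders | upper | 0.0049 | 0.0049 |
| 89 (50.9%) | 89 responders | lower | 0.0088 | 0.994 |
| 88 (50.3%) | 88 responders | lower | 0.0058 | 0.996 |
| 54 (30.9%) | 121 non-responders | upper | 0.0077 | about 1 |

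At 54/175 responders the code would show an estimate of 121/175 = 69.1% with a lower limit of 61.7%. That is the same output as for 121 responders, the smallest count that truly passes at 0.0083.

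**Step 4: all wrong-pass counts, from x = 0 to n.**

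| n | Level 0.0083 | Level 0.025 |
|---|---|---|
| 140 | 0–41 | 0–44, 68–72 |
| 161 | 0–49, 80–81 | 0–51, 78–83 |
| 175 | 0–54, 87–88 | 0–56, 84–91 |

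Level 0.025 applies only after the other two tests have passed.

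**Step 5: probability of a wrong pass at level 0.0083**, summing binomial probabilities over those counts and excluding correct rejections.

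| True rate | n = 175 | n = 140 |
|---|---|---|
| 0.30 | 63% | 47% |
| 0.40 | 1.1% | 0.5% |
| 0.50 | 12% | about 0 |
| 0.55 | 5.0% | about 0 |
| 0.60 | 0.3% | about 0 |
| 0.75 | about 0 | about 0 |

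At a true rate of 0.60 and n = 175, correct rejections have probability 0.8%, so the total rises from 0.8% to 1.1%.

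**Step 6: each assumption alone (n = 175, level 0.0083).** With A alone and an upper tail throughout, wrong passes occur at 54 or fewer. With B alone and responders always tested, they occur at 88 or fewer. So the conclusion does not need both assumptions, and repairing only one part leaves the other exposed.

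**Step 7: above 60%.** For every count with x/n > 0.6, the printed and correct p-values are identical. No true rejection is lost.

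**The case against.** The strongest reply has three parts.

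- **The size depends on recalled software behaviour.** The documents alone show only that no level and no tail are given. This is correct, and the figures are conditional on it. Standard output might also print the frequency table and label the tested level and the tail, which would help a careful reader.
- **The decision rule is already directed.** SAP 7.1.1 defines p for responders and describes a pass as a responder rate significantly above 60%. A lower-tail or non-responder p-value is not the p-value of that hypothesis, so using it would breach the text. The section also requires responder counts and percentages. At 54/175 that table shows 30.9%. At 87 or 88 responders the code's own limits, about 42.6% to 57.9%, lie wholly below 60%.
- **The affected range is far from the plan.** At 0.75 the probability is about 0, and the 63% figure needs a true rate of 0.30.

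All of this limits the consequence. None of it makes the code correct: the SAP prescribes it for the confirmatory analysis, and it need not return the p-value or the interval that the same section promises. Relying on another table to catch the discrepancy is a safeguard outside the specified test.

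**Conclusion.** The concern holds. As written, the prescribed code does not guarantee the test in SAP 7.1.1, because the data may choose the category and no upper tail is set. That much follows from the documents.

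The size rests on two stated assumptions about PROC FREQ, and on the printed one-sided p-value being taken into Holm's procedure without a check of direction. Under these conditions the damage is confined to observed rates of 60% or less. At n = 175 and level 0.0083 that means 54 or fewer responders, or 87–88. The hypotheses, the significance levels, the sample size, the stated power and any result above 60% are untouched. It should be corrected, but it does not threaten the trial if response is near the expected 75%.

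**What to change.** Remove the frequency ordering and name the responder level, for example `tables response / binomial(p=.6 level='Responder' cl=exact) alpha=.05`, with the level written as the variable is actually coded. Add one sentence: Holm's procedure uses the upper-tail exact p-value P(X ≥ x | n, 0.6) for responders, and the lower 97.5% Clopper-Pearson limit for the responder rate is reported.

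Naming the level is not enough by itself. If the tail still followed the data, the one-sided p-value would fall below 0.0083 at every count of 88 or fewer out of 175.

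The cost is one line of SAP code and one sentence. Sample size and power stay as planned, and there is no downside.
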